4.6.3 Additional Safety Analyses Performed for COVID-19

From MedDRA 25.0, a COVID-19 SMQ (narrow) is available. This SMQ includes the preferred terms relevant to COVID-19 infection, and these terms will be used to assess the impact of COVID-19. Patients with AEs from this COVID-19 SMQ (narrow) will be considered to have a confirmed or suspected COVID-19 infection.

A listing of all confirmed and suspected COVID-19 Adverse events will be produced.

In addition to presenting the suspected/confirmed COVID-19 infections, a listing of AEs associated with COVID-19 during the study will be presented. An AE associated to COVID-19 is defined as an AE reported ≤7 days before and ≤30 days after any reported AE suggesting a confirmed COVID-19 infection according COVID-19 SMQ (narrow).

4.6.4 Ocular assessments

Results of the following ocular assessments will be summarized by time point, using descriptive summaries and graphical presentations (If applicable):

- Intraocular pressure (IOP)
- Slit lamp examination
- Indirect Ophthalmoscopy

Changes from Baseline in pre-dose IOP measurements and changes between pre-dose and post-dose IOP measurements will be summarized.

The presence of Anterior chamber cell, Vitreous cell, Vitreous hemorrhage, Anterior chamber flare and cataract as determined on slit lamp examination will be tabulated by grade (according to grading scales for flares and cells in Appendix 3 of Protocol Version 4).

The presence of posterior vitreous detachment or retinal break or detachment as determined from ophthalmoscopy will be tabulated. The type of retinal detachment (i.e. involving or not macula) will be also described.

4.6.5 Laboratory Data

Pregnancy Test:

Pregnancy test results collected will be listed as "positive" or "negative" with the date of the pregnancy test for women with a pregnancy test recorded.

HbA1c results:

HbA1c will be summarized at baseline, week 16 and week 24 visit using descriptive statistics. Data from other unscheduled assessments will not be included in this summary or analysis.

Descriptive statistics will be used to summarize the following:

- HbA1c at baseline, at week 16 and week 24
- Hba1c in categories (< 6.5 %, ≥ 6.5 < 8 % and ≥ 8%)

A listing of HbA1c at each visit will be also presented.

4.6.6 Vital Signs

Vital signs will be collected at screening, Safety Follow-up visit only. These data can be used for interpretation of some AEs, no general summary is planned.

4.6.7 Concomitant medications

Concomitant medications (defined as treatment started on or after baseline visit or treatment started before baseline visit and ended/ongoing during the treatment period) will be summarized by frequency tables according to the Anatomic Therapeutic Chemical (ATC) classification system using the WHO Drug dictionary.

Medication with a partial start date will be considered as concomitant except if the end date is before study treatment date.

A listing of ocular concomitant medications in the study eye will be presented.

4.6.8 Concurrent ocular procedures

Number and percentages of patients with concurrent ocular procedures as well as the Disease category of concurrent ocular procedures will be tabulated (study eye, fellow eye analyzed separately).

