Complications for AH sampling reported in the literature are traumatic injuries of the iris, hyphema, inflammation, infection, and hypotension. The reported complication rates are between 0.01% and 0.7% with no long-term sequelae and no effect on VA (Saxena et al. 2019; Trivedi et al. 2011). There is also a small risk of induction of traumatic cataract associated with AC paracentesis (Pleyer and Garweg 2008).

The planned multimodal imaging assessments are considered as part of the current SOC. They are routinely used in the clinic for diagnosis, assessment of the disease course, response to treatment, and for research purposes to better understand the underlying disease pathology. All instruments used will be American National Standards Institute compliant.

Based on the results of the Phase II study (BP30099 [BOULEVARD]), the 6-mg dose of faricimab has the potential for superior efficacy outcomes in DME and the potential for prolonged treatment duration while achieving and maintaining comparable efficacy when compared to SOC IVT. Besides close monitoring and treatment with faricimab, no other direct benefits are foreseen for the patients. However, patients in this study will provide AH biomarker samples and associated data to generate algorithms that could potentially lead to a more personalized treatment option for future patients.

In the setting of the coronavirus 2019 (COVID-19) pandemic, patients with comorbidities including those patients with diabetes are a more vulnerable population. Infection with severe acute respiratory syndrome coronavirus 2 (SARS-CoV-2) has been associated with higher morbidity and mortality in patients with diabetes in some retrospective analysis. Susceptibility to infection with diabetes may be argued, but infection once acquired is likely to be more severe and prolonged, determined by a number of factors, including duration of diabetes, the presence of diabetes-related complications, and the level of glycemic control. It is not anticipated that faricimab will increase the risk of infection with SARS-CoV-2. Four Phase 3 clinical trials (2 in DME and 2 in nAMD) with faricimab are ongoing during this pandemic, and to date these studies have not shown any increased risk of developing COVID-19 or of having a worse outcome in patients on faricimab, however this will continue to be monitored.

2. OBJECTIVES AND ENDPOINTS

The exploratory objective and the endpoints are provided in Table 1.

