4.4.1 Permitted Therapy

Patients who use concomitant medications should continue their use. Of note, the following are some common therapies that are permitted:

- Onset of ocular hypertension or glaucoma in the study eye during a patient's study participation should be treated as clinically indicated.
- Onset of cataract or posterior capsular opacification in either eye during a patient's study participation may be treated as clinically indicated. Dose interruption criteria (see Section 5.1.2.2, Section 5.1.2.3, and Table 3 may apply if cataract surgery is required.
- Short-term use of topical ocular corticosteroids after cataract surgery, yttrium-aluminum garnet capsulotomy, peripheral iridotomy, argon/selective laser trabeculoplasty, or ocular allergic conditions.

Fellow (Non-Study) Eye Treatment with Anti-VEGF Therapy

At the discretion of the investigator, the patient's fellow eye (non-study eye) may be treated with anti-VEGF therapy licensed for ocular use if they are diagnosed with an ocular condition for which the selected anti-VEGF therapy (except brolucizumab) is approved by the country regulatory agency (SOC). Should the fellow eye require treatment during the study, the Sponsor will cover the cost of the approved licensed ocular anti-VEGF therapy (except brolucizumab and Susvimo ™) in accordance with local regulations, until faricimab is made available in that region, after which the Sponsor will support fellow-eye treatment with faricimab as long as the patient remains in the study. Any exceptions for ongoing reimbursement of other anti-VEGF therapies must be approved by the Sponsor.

Fellow eye treatment reimbursement will cease if the patient is discontinued from faricimal study treatment. Fellow eye treatment reimbursement will cease once the patient has completed the trial.

Study eye treatment and fellow eye treatment with anti-VEGF agents may be done at the same study visit; however, the study eye should receive study treatment per protocol

prior to anti-VEGF treatment in the fellow eye. *Note: Bevacizumab is not licensed for ophthalmic use in any country; therefore, it is prohibited to be used.*

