5.1.1 Risks Associated with Faricimab

The anticipated safety risks for faricimab are outlined below; these risks are either from the drug itself or the injection procedure.

Anticipated risks of faricimab include intraocular inflammation, the IVT injection-related risks of infectious endophthalmitis, retinal detachment/tear, and *transient* increased IOP. Potential risks *associated with faricimab include* iatrogenic traumatic cataract, *immunogenicity*, as well as the non-ocular risk of arterial thromboembolic events.

Please see the RO6867461 (faricimab) Investigator's Brochure for more details on the *safety information for* faricimab.

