Appendix 3 Grading Scale for Assessment of Anterior Chamber Flare or Cells and Vitreous Cell

Anterior Chamber Flare	
Grade	Description
0	None
1+	Faint
2+	Moderate (iris and lens details clear)
3+	Marked (iris and lens details hazy)
4 +	Intense (fibrin or plastic aqueous)

Anterior Chamber Cells					
Grade	Cells in Field ^a				
0	< 1				
0.5 +	1–5				
1+	6–15				
2+	16–25				
3 +	26–50				
4+	> 50				

^a Field size is a 1-mm slit beam.

Vitreous Cells						
Grade	Number of Vitreous Cells					
0	No cells					
0.5 +	1–10					
1+	11–20					
2+	21–30					
3+	31–100					
4 +	> 101					

From: The Standardization of Uveitis Nomenclature (SUN) Working Group criteria.

REFERENCE

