4.3 DEMOGRAPHIC AND BASELINE CHARACTERISTICS

Baseline is defined as the last available measurement obtained on or prior to the day of first dose. Patients with missing baseline assessments will not be imputed.

The following demographic and baseline characteristics will be summarized for the mITT population:

- Age (years) as continuous variable and age in category < 65 years, ≥ 65 years
- Gender (Male and Female)
- Self-reported race and ethnicity
- Region
- Female reproductive status
- Smoking history (never, current, former)
- Diabetes mellitus (Type 1, Type 2)
- Baseline HbA1c as continuous and in category < 6.5 %, ≥ 6.5 < 8 % and ≥ 8%
- Systolic blood pressure (mmHg) as continuous variable and its category <140 mmHg, >=140 and <160 mmHg and >=160 mmHg
- Diastolic blood pressure (mmHg) as continuous variable
- Blood pressure (mmHg) in category (> 160 systolic or > 90 diastolic, <= 140 systolic and <= 85 diastolic and <= 120 systolic and <= 80 diastolic)

Baseline ocular characteristics:

- Baseline ocular characteristics description will be done in study eye and fellow eye (analyzed separately).
 - Study eye selection (Eligible eye (right, left, bilateral) and selected eye (right, left)).
 - Diabetic macular edema (Yes/No) (for fellow eye only)

- Diabetic macular edema status at baseline (Resolved/Ongoing) (for fellow eye only)
- Duration since Diabetic macular edema initial diagnosis Onset (in months) and its category (≤ 3 months and >3 months) (date of baseline visit – onset date of Diabetic macular edema diagnosis +1) / 30.4375.
- Baseline BCVA
- Baseline ocular assessments
 - Center subfield thickness (CST)
 - Macular Ischemic Non-Perfusion (Yes/No): Absence is defined as Total area of capillary non perfusion within the macula of 0 to 0.1 mm2.
 - Macular leakage (Yes/No): Absence is defined as Total area of fluorescein leakage within the macula of 0 mm2
 - Intraocular Pressure (mmHg)
 - Lens status (phakic, pseudophakic, aphakic, other)
 - Global Diabetic retinopathy status (ETDRS scale into 12 step) from Ultra-widefield Fundus Photography (UWF-C)
 - Diabetic retinopathy status (ETDRS scale into 12 step) from Color Fundus Photography (FP-7M

A listing of Demographics and relevant baseline characteristics will be presented.

General medical history and baseline conditions:

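### The slit lamp cataract table in SAP 4.6.4 shows presence at each visit, so it cannot show new or worsened cataract in the eyes at risk (low priority)

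*SAP*

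**What the plan says.** Protocol 5.1.1 lists "iatrogenic traumatic cataract" among the potential risks of faricimab. Protocol 1.3.2 adds, for the aqueous humor sampling: "There is also a small risk of induction of traumatic cataract associated with AC paracentesis". Each study eye is scheduled for six injections and two taps (Protocol Appendix 1).

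For the slit lamp data, SAP 4.6.4 states: "Results of the following ocular assessments will be summarized by time point". Cataract is in the list of findings whose presence is reported: "Anterior chamber flare and cataract as determined on slit lamp examination will be tabulated by grade". The grading is given as "according to grading scales for flares and cells in Appendix 3 of Protocol Version 4". That appendix is headed "Grading Scale for Assessment of Anterior Chamber Flare or Cells and Vitreous Cell" and contains no cataract scale. Change from baseline is specified in SAP 4.6.4 for intraocular pressure only.

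SAP 4.6 bases all safety analyses on the safety-evaluable population, meaning everyone who received at least one injection (SAP 4.1.4). SAP 4.3 summarizes lens status at baseline for each eye, but SAP 4.6.4 does not use it. On treatment during the study, Protocol 4.4.1 says: "Onset of cataract or posterior capsular opacification in either eye during a patient's study participation may be treated as clinically indicated".

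**The concern.** A count of eyes with cataract at each visit is a prevalence. The question raised by the named risk is how many eyes that could develop a cataract did so, or got worse. Prevalence answers that poorly for three reasons:

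- **Cataract at entry.** Exclusion criterion 35 removes only significant cataract that also meets one of three further conditions. Eyes with milder cataract can enter and would count as present from the start.
- **Eyes not at risk.** Exclusion criterion 28 bars intraocular surgery only within 3 months before Day 1 or if planned, so pseudophakic eyes can enter. They cannot develop the event but may stay in the denominator.
- **Operated eyes.** If a cataract is removed on study, the eye may move from present to absent. The SAP does not say how such an eye is coded.

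At stake is whether the one lens-specific safety table can be read as evidence about a harm that the protocol names for both study procedures.

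**Working it through.** The plan states no cataract rate, phakic share or number of operations, so there is no figure to reproduce. The check traces the planned outputs and then illustrates the size with assumed inputs.

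**1. What each planned output can show**

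| Output | New or worsened separated from pre-existing? | Operated eye kept visible? | At-risk denominator? |
|---|---|---|---|
| Slit lamp table (SAP 4.6.4) | No; visit columns give no within-eye change | Not specified | Not specified |
| Treatment-emergent AEs by eye, SOC and PT (SAP 4.6.2) | Yes, if reported: onset on or after first dose, or increased intensity | Yes, if reported as an AE | No |
| Concurrent ocular procedures by eye (SAP 4.6.8) | No; counts procedures and disease category | Yes | No |

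No row gives a proportion among eyes at risk.

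**2. Dilution.** With x events in N eyes, of which a share f is phakic, the all-eyes rate is x/N and the at-risk rate is x/(fN). Their ratio is 1/f. Assumed f:

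- f = 0.60: 1/0.60 = 1.67
- f = 0.75: 1/0.75 = 1.33
- f = 0.90: 1/0.90 = 1.11

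**3. Mixing and loss.** Take N = 99 (SAP 2.3). Assume a non-phakic share p, a share c of phakic eyes with cataract at baseline, a 5% risk of new cataract in phakic eyes without one, and k operated cataracts.

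- Baseline count B = N(1 − p)c; eyes without cataract R = N(1 − p)(1 − c); new cases = 0.05R.
- Change in visit prevalence = (0.05R − k)/N.

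Middle case, p = 0.2 and c = 0.4: B = 99 × 0.8 × 0.4 = 31.7, R = 47.5, new = 2.4. Prevalence goes from 31.7/99 = 32.0% to 34.1/99 = 34.4%, a rise of 2.4 points where the risk is 5%.

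Over p = 10% to 40% and c = 20% to 60%, with k = 0, the rise is 1.2 points (p = 0.4, c = 0.6: 1.19/99) to 3.6 points (p = 0.1, c = 0.2: 3.56/99). With k = 3 and operated eyes leaving the count, the net change is −1.8 to +0.6 points.

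If only new cataracts are operated, k cannot exceed the number of new cases and the net change cannot be negative. A fall therefore requires operations on cataract that was present at entry.

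**4. Precision.** Three events in 60 phakic eyes give 5.0%, with a Clopper-Pearson 95% interval of 1.0% to 13.9%. That is far wider than a dilution factor of 1.1 to 1.7.

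**The case against.** The strongest reply is that the plan already counts new and worsened cataract elsewhere. Protocol 5.3.5.8 makes a pre-existing condition an adverse event only if it worsens. SAP 4.6.2 tabulates treatment-emergent ocular events by eye and preferred term, so cataract would have its own row, and it separately reports study-eye events related to treatment. Recording of adverse events is mandatory, with assessment by the retinal physician (Protocol 5.3), and the slit lamp examination is done at every visit. Operated eyes appear in the procedures table. The study is exploratory and single-arm, its safety analysis is descriptive, and no at-risk estimate was promised.

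Most of this stands, and it rules out several stronger readings:

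- *That an operated cataract vanishes from the safety record.* At most it leaves the slit lamp table.
- *That the table will be over all eyes.* This is inferred from the population and the absence of a restriction; the SAP is silent.
- *That the table would probably show a fall while new cataracts occur.* Criteria 28 and 35 largely screen out the operations on pre-existing cataract that this needs.
- *That cataract alone lacks a dedicated adverse event group.* Transient raised intraocular pressure and immunogenicity, also named in Protocol 5.1.1, have none either.
- *That a phakic-eye rate would measure iatrogenic traumatic cataract.* Without a control it also contains natural lens progression.

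What the reply does not answer is that the slit lamp table cannot show within-eye change, that the adverse event route depends on what is reported, and that no output uses eyes at risk. The missing cataract grade is a separate documentation gap in the same sentence and remains whatever view is taken of the rest.

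**Conclusion.** The point holds as a limitation of one table, not as a gap in the collection of cataract safety data. The slit lamp output in SAP 4.6.4 cannot distinguish new or worsened cataract from cataract at entry, leaves the eye and denominator unstated, has no rule for operated eyes, and refers to grades that the cited appendix does not define for cataract.

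Its size cannot be taken from the documents. The factor of 1.7 to 1.1 rests entirely on an assumed phakic share of 60% to 90% and on the table being run over all eyes. Event numbers will be small and any rate imprecise. Priority is low: an inexpensive improvement that the sponsor could make.

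**What to change.** In SAP 4.6.4, replace the cataract part of the sentence with wording to this effect:

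> For study eyes phakic at baseline, cataract status or grade will be shown in a shift table from baseline to the worst post-baseline slit lamp examination. The number and percentage of these eyes with new or worsened cataract will be given with a two-sided 95% Clopper-Pearson interval. Eyes with cataract surgery on study will be shown in a separate row, split by whether cataract was present at baseline. The percentage includes natural lens progression and is not attributable to the injection or the tap.

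Name the cataract grading used, or report presence only if no grade is collected.

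The change uses slit lamp, lens status and procedure data that the plan already summarizes. It alters no study procedure or treatment rule. The cost is a few lines of SAP text and one extra table, with a smaller denominator and a less favorable-looking rate.

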4.7 MISSING DATA

For exploratory and safety analyses, missing data will not be imputed, except for the MMRM analyses where missing data will be implicitly imputed by the MMRM model, assuming a missing at random missing data mechanism. The data will be used up to discontinuation.

4.8 INTERIM ANALYSES

As this is an open-label study, no formal interim analyses are planned. Exploratory analyses of selected endpoints may be performed during the course of the study (e.g., after all patients have completed the Day 28 visit and the necessary data are available).

Appendix 1 Protocol Synopsis

PROTOCOL SYNOPSIS

TITLE: AN EXPLORATORY, PROSPECTIVE, MULTI CENTER, OPEN-

LABEL, SINGLE-ARM, INTERVENTIONAL, PHASE IIB STUDY TO INVESTIGATE AQUEOUS HUMOR AND MULTIMODAL IMAGING

BIOMARKERS IN TREATMENT-NAÏVE PATIENTS WITH DIABETIC MACULAR EDEMA TREATED WITH FARICIMAB

(RO6867461) - ALTIMETER STUDY

PROTOCOL NUMBER: MR41926

VERSION NUMBER: 4

EUDRACT NUMBER: 2020-001174-30

IND NUMBER: 119,225

NCT NUMBER: NCT04597918

TEST PRODUCT: Faricimab (RO6867461)

PHASE: IIb

INDICATION: Diabetic macular edema (DME)

SPONSOR: F. Hoffmann-La Roche Ltd

Objectives and Endpoints

This is an exploratory, prospective, multicenter, open-label, single-arm, interventional, Phase IIb study designed to explore the associations over time between clinical assessments, multimodal imaging assessments, aqueous humor (AH) biomarker patterns, and genetic polymorphisms in patients with DME who are treated with faricimab (RO6867461). The exploratory objective and endpoints for the study are outlined in the following table.

Objectives and Corresponding Endpoints

Exploratory Objective	Exploratory Endpoints	
To explore the associations over time between clinical assessments, multimodal imaging assessments, AH biomarker patterns, and genetic polymorphisms	 Proportion of patients with a ≥2-step ETDRS DRSS improvement over time Proportion of patients with a ≥3-step ETDRS DRSS improvement over time Changes from baseline on the ETDRS DRSS over time Changes from baseline in BCVA (as measured on the ETDRS chart) over time Changes from baseline in IRF over time Changes from baseline in SRF over time Changes from baseline in CST over time Changes from baseline in multimodal imaging over time including: FAZ, ischemic index, ischemic area, and MAs (location and number) CST, IRF, SRF, HRF, cyst reflectivity, and DRIL in OCT en-face and volumes Changes from baseline in AH biomarker patterns over time including: Proteins, including but not limited to: cytokines, chemokines, and growth-, angiogenesis-, and complement-related factors, etc. Metabolites, including but not limited to: lipids, sugars, amino acids, etc. Genetic polymorphisms via standard clinical genotyping Advanced analytics tools (e.g., artificial intelligence-based tools) for the assessment of clinically relevant features 	

AH=aqueous humor; BCVA=best-corrected visual acuity; CST=central subfield thickness; DRIL=disorganization of retinal inner layers; DRSS=Diabetic Retinopathy Severity Scale; ETDRS=Early Treatment Diabetic Retinopathy Study; FAZ=foveal avascular zone; HRF=hyper-reflective foci; IRF=intraretinal fluid; MA=microaneurysm; OCT=optical coherence tomography; SRF=subretinal fluid.

Study Design

Description of Study

This is an exploratory, prospective, multicenter, open-label, single-arm, interventional, Phase IIb study designed to explore the associations over time between clinical assessments, multimodal imaging assessments, AH biomarker patterns, and genetic polymorphisms in patients with DME who are treated with faricimab (RO6867461). All DME patients enrolled will be treatment-naïve in the study eye. Hypothesis-generating signals will be assessed via associations in visual function, retinal anatomy, and AH protein/metabolite composition. State-of-the-art imaging technologies and new immunoassay platforms will be utilized in this study. Advanced analytics and multivariate analysis will also be used to show the relationships between AH and imaging biomarkers as well as genetic polymorphisms.

- AH taps from the study eye will be collected on Day 1 (baseline) and the Day 112 visit (i.e., prior to injections 1 and 5).
- Multimodal retinal imaging will be applied at the screening visit, Day 1 (baseline), and throughout the study.

Patients will receive 6 doses (one 6 mg faricimab intravitreal [IVT] injection every 28 days [Q4W]) starting at Day 1 and ending on the Day 140 visit. Patients will return for a safety follow up visit (SFV) after ≥ 28 days and within < 35 days following their last study treatment. Patients

who discontinue from the study or treatment early (prior to the SFV), but have not withdrawn consent (and have not been lost to follow-up) should return for an early termination visit (ETV) after ≥28 days have elapsed following their last study treatment (visit should occur within < 35 days of the patient's last study treatment).

Data from adaptive optics (AO) instruments will be collected from selected study sites that have the technology available. The purpose of this data collection is to conduct a feasibility test of AO for future studies.

In this study, the ocular inclusion and exclusion criteria for the study eye require an assessment of diabetic retinopathy (DR) severity as assessed on the ETDRS DRSS. If both eyes are considered eligible, the eye with the worse BCVA, as assessed at screening, will be selected for the study eye unless the Investigator deems the other eye to be more appropriate for treatment in the study.

Patients who use concomitant medications should continue their use, unless listed as a prohibited therapy for this study. Patients who receive prohibited therapies may be discontinued from the study treatment and/or the study.

Patients who discontinue the study prematurely will not be replaced and will not be allowed to restart study treatment.

Screening

The Informed Consent Form (ICF) must be administered and signed by a patient before any study-specific screening procedure is performed. Each consented patient must satisfy the eligibility criteria at screening. The screening evaluation will be performed within 28 days preceding the baseline visit (the day of the first study treatment).

Screen-Failed Patients

Screen failures are defined as patients who consent to participate in the clinical study but are subsequently not entered in the study.

The Investigator will maintain a *detailed* record of all patients screened and *will document* eligibility or record reasons for screening failure.

Participants that do not meet one or more of the inclusion criteria are considered screen failure, no re-screening is permitted. However, screen-failed patients (due to only the protocol version 1.0 and 2.0 DRSS criteria) that meet all of the inclusion criteria after the protocol amendment v3.0/v3.1 could be re-screened. *In this situation the following scenarios are to be applied:*

- 1. Due to a significant change in the screening criteria being unlikely that features assessed for eligibility change within one month and to reduce patient burden during a pandemic, screening assessments (including ocular imaging) do not have to be repeated at re-screening as long as the re-screening assessment occurs within 28 days after the initial screening.
- 2. If the re-screening assessment is performed more than 28 days after the initial screening visit, all assessments will be re-performed; with the exception of ultra wide field (UWF)-fundus fluorescein angiography (FFA) that does not need to be redone if the previous UWF-FFA was performed within ≤2 months (56 days) of the new screening day.

In case the central reading center cannot determine Inclusion criteria 7 (DME) and exclusion criteria 22 (ETDRS DRSS) due to poor quality of the retinal images, the image acquisition may be repeated for screening purposes (allowed once) but has to be *in consultation* with the Medical Monitor. Regarding screening number and ICF signature, the below described scenarios should be followed.

Regarding exclusion criteria, a screening may result in 1 of the following 4 scenarios:

The patient meets 1 or more of the exclusion criteria that will not change (e.g., any history
of idiopathic, infectious, or noninfectious uveitis). Such a patient would be a screen failure
and no re-screening is permitted.

- The patient is eligible, but misses the 28-day window from the screening visit to enrollment on Day 1 due to logistical reasons. Such a patient must be re-screened (all assessments will be performed; exception UWF-FFA does not need to be redone if the previous UWF-FFA was performed within ≤2 months [56 days] of the new screening day), assigned a new screening number through interactive voice or web-based response system (IxRS) (treated as new patient), and re-sign the ICF prior to re-screening.
- The patient meets 1 or more of the exclusion criteria that may change (time-dependent) and allow(s) for re-screening (e.g., use of any systemic corticosteroids within 1 month prior to Day 1). Such a patient can be re-screened for the criterion/criteria in question within the 28-day screening window and will maintain the same screening number. A full list of applicable criteria is given below. Re-screening is permitted only for the exclusion criteria that include the following statement: "One re-screening for this criterion is permitted."
- Patient meets 1 or more of the exclusion criteria that may change (time-dependent) and allow(s) for re-screening (e.g., use of any systemic corticosteroids within 1 month prior to Day 1). If such a patient cannot be re-screened for the criterion/criteria in question within the 28-day screening window, a complete new screening is required (all assessments will be performed; exception UWF-FFA does not need to be redone if the previous UWF-FFA was performed within ≤2 months [56 days] of the new screening day), patients will be assigned a new screening number through IxRS (treated as new patient), and patients must re-sign the ICF prior to re-screening. Re-screening is permitted only for the exclusion criteria in that include the following statement: "One re-screening for this criterion is permitted."

A maximum of 1 re-screening per patient (for a total of 2 screenings per patient) will be allowed.

Number of Patients

Approximately 35 global study sites will enroll approximately 80 patients who are treatment-naı̈ve in the study eye. However, the Sponsor may increase the sample size up to 100 patients, to compensate for those patients who completed the study without having a full set of Day 1 (baseline) and Day 112 visit analyzable AH samples collected. The aim of this increase is to achieve 60 patients with analyzable Day 1 (baseline) and Day 112 visit AH samples. The Sponsor may decide to stop the enrollment as soon as the target of 60 analyzable sets of AH samples is reached.

Target Population

Inclusion Criteria

Patients must meet all of the following criteria for study entry:

Informed Consent

- 1. Signed ICF prior to any study-related assessments
 - All patients are able and willing to provide written informed consent and to comply with the study protocol according to International Council for Harmonisation (ICH) and local regulations.
 - Patients are willing to allow AH collection and in the opinion of the Investigator, sampling of >90 µl of AH seems feasible and safe.
- 2. Ability to comply with the study protocol, in the Investigator's judgment

Age

3. Age ≥18 years at the time of signing the ICF

Type of DME Patients and Disease Characteristics

- 4. Diagnosis of diabetes mellitus (Type 1 or Type 2), as defined by the World Health Organization (WHO) and/or American Diabetes Association and
 - Current regular use of insulin or other injectable drugs (e.g., dulaglutide and liraglutide) for the treatment of diabetes
 - · Current regular use of oral anti-hyperglycemic agents for the treatment of diabetes

- 5. Hemoglobin A_{1c} (HbA_{1c}) ≤10% (historic values up to 2 months before the screening visit will be permissible; otherwise, the study site may collect a sample for analysis at screening)
- 6. Patients who are IVT treatment-naïve in the study eye (i.e., have not received previous treatment with any anti-vascular endothelial growth factor-A (VEGF-A) IVT or any corticosteroids periocular or IVT in the study eye).

Ocular Inclusion Criteria for Study Eye

- 7. DME defined as macular thickening by spectral-domain optical coherence tomography (SD-OCT) involving the center of the macula: CST of ≥ 325 µm with Spectralis® (Heidelberg Engineering, Heidelberg, Germany) at screening. This inclusion criterion is to be assessed by the central reading center (CRC).
- 8. Decreased VA attributable primarily to DME, with BCVA letter score of 75 to 20 letters (both inclusive) on ETDRS-like charts at the screening visit
- 9. Clear ocular media and adequate pupillary dilation to allow acquisition of good quality retinal images to confirm diagnosis

Contraception

- 10. For women of childbearing potential (WOCBP): agreement to remain abstinent (refrain from heterosexual intercourse) or use contraception as defined below:
 - Women must remain abstinent or use contraceptive methods with a failure rate of < 1% per year during the treatment period and for at least 3 months after the final dose of faricimab.
 - A woman is considered to be of childbearing potential if she is postmenarchal, has not reached a postmenopausal state (≥ 12 continuous months of amenorrhea with no identified cause other than menopause), and is not permanently infertile due to surgery (i.e., removal of ovaries, fallopian tubes, and/or uterus) or another cause as determined by the Investigator (e.g., Müllerian agenesis). The definition of childbearing potential may be adapted for alignment with local guidelines or regulations.
 - Examples of contraceptive methods with a failure rate of < 1% per year include bilateral tubal ligation, male sterilization, hormonal contraceptives that inhibit ovulation, hormone-releasing intrauterine devices, and copper intrauterine devices.
 - Contraception methods that do not result in a failure rate of < 1% per year such as male
 or female condom with or without spermicide; and cap, diaphragm, or sponge with
 spermicide are not acceptable.
 - The reliability of sexual abstinence should be evaluated in relation to the duration of the
 clinical study and the preferred and usual lifestyle of the patient. Periodic abstinence
 (e.g., calendar, ovulation, symptothermal, or postovulation methods) and withdrawal are
 not adequate methods of contraception. If required per local guidelines or regulations,
 locally recognized adequate methods of contraception and information about the
 reliability of abstinence will be described in the local ICF.

Exclusion Criteria

Patients who meet any of the following criteria will be excluded from study entry:

Medical Conditions

- 1. Currently untreated diabetes mellitus or previously untreated patients who initiated oral or injectable anti-diabetic medication within 3 months prior to Day 1.
- 2. Any known hypersensitivity to any of the components in the faricimab injection.
- 3. Any known hypersensitivity to any contrast media (e.g., fluorescein), dilating eye drops, or any of the anesthetics and antimicrobial preparations used by the patient during the study.
- 4. Any major illness or major surgical procedure within 1 month before the Day 1. One re-screening for this criterion is permitted.
- 5. History of other diseases, other non-diabetic metabolic dysfunction, physical examination finding, historical or current clinical laboratory finding giving reasonable suspicion of a condition that contraindicates the use of the faricimab or that might affect interpretation of

- the results of the study or renders the patient at high-risk for treatment complications, in the opinion of the Investigator.
- 6. Active cancer within the past 12 months prior to Day 1 except for appropriately treated carcinoma in situ of the cervix, non-melanoma skin carcinoma, and prostate cancer with a Gleason score of ≤6 and a stable prostate-specific antigen for >12 months.
- 7. Stroke or myocardial infarction within 12 months prior to the Day 1. One re-screening for this criterion is permitted.
- 8. Any febrile illness within 1 week prior to Day 1. One re-screening for this criterion is permitted.
- 9. Pregnant or breastfeeding, or intending to become pregnant during the study or within 3 months after the final dose of faricimab.
 - WOCBP must have a negative serum pregnancy test result within 28 days prior to initiation of faricimab and a negative urine pregnancy test at the baseline visit.
- 10. Uncontrolled blood pressure (BP); defined as systolic > 180 mmHg and/or diastolic > 100 mmHg (while patient at rest). If a patient's initial reading exceeds these values, a second reading may be taken ≥ 30 minutes later on the same day. If the patient's BP is controlled by antihypertensive medication, the patient should be taking the same medication continuously for at least 30 days prior to Day 1. One re-screening for this criterion is permitted.
- 11. Renal failure requiring renal transplant, hemodialysis, or peritoneal dialysis within 6 months prior to Day 1 or anticipated to require hemodialysis or peritoneal dialysis at any time during the study.
- 12. Any condition resulting in a compromised immune system that is likely to impact the AH inflammatory biomarkers. In case of doubt, the Investigator should consult with the Medical Monitor.

Prior/Concomitant Therapy

- 13. Patients who are currently enrolled in or have participated in any other clinical study involving an investigational product or device, or in any other type of medical research, within 3 months or 5 half-lives (whichever is longer) prior to Day 1 and up to completion of the current study. One re-screening for this criterion is permitted.
- 14. Substance abuse occurring within 12 months prior to screening, in the Investigator's judgment.
- 15. Use of systemic immunomodulatory treatments (e.g., IL-6 inhibitors) within 6 months or 5 half-lives (whichever is longer) prior to Day 1. One re-screening for this criterion is permitted.
- 16. Use of any systemic corticosteroids (including inhaled corticosteroids from inhalers used regularly (e.g., pulmonary disease, asthma, or seasonal allergy) within 1 month prior to Day 1. One re-screening for this criterion is permitted.

 Note: Subjects using inhaled corticosteroids occasionally (PRN); PRN use of inhaled corticosteroids is permitted if a 3-day period of abstinence between corticosteroid inhalation and study visit is respected.
- 17. Systemic treatment for suspected or active systemic infection.

 Note: Ongoing use of prophylactic antibiotic therapy may be acceptable but has to be *in consultation* with the Medical Monitor.
- 18. Any prior or concomitant systemic anti-VEGF treatment within 6 months or 5 half-lives (whichever is longer) prior to Day 1. One re-screening for this criterion is permitted.
